5.2 Selection of Study Population

Approximately 325 subjects (65 subjects per arm), from approximately 60 study sites in the US, hospitalized for liver cirrhosis and OHE, with a HEGI score of 2 or 3 following adequate hydration and lactulose treatment, will be enrolled in this clinical investigation. Expansion to other countries may be considered.

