5.2.1 Eligibility

5.2.1.1 Inclusion Criteria

A subject will be eligible for inclusion in this study if he/she meets all of the following criteria:

1. Male or female at least age 18 or older at the time of consent.
2. Female subjects of childbearing potential, defined as fertile following menarche, must have a negative serum pregnancy test at screening and agree to use an acceptable method of contraception throughout their participation in the study. NOTE: Serum pregnancy tests performed upon hospital admission, prior to time of consent, may be used at Screening. Acceptable methods of contraception include double barrier methods (condom with spermicidal jelly or a diaphragm with spermicide), hormonal

methods (e.g., oral contraceptives, patches or medroxyprogesterone acetate), or an intrauterine device (IUD) with a documented failure rate of less than 1% per year. Abstinence or partner(s) with a vasectomy may be considered an acceptable method of contraception at the discretion of the investigator. See [Section 5.2.2](#) for additional information.

Note: Female subjects who have been surgically sterilized (e.g., hysterectomy or bilateral tubal ligation) or who are postmenopausal (defined as a total cessation of menses for > 1 year) will not be considered “female subjects of childbearing potential”.

3. Subject is hospitalized with encephalopathy secondary to liver cirrohis and has a confirmed diagnosis of OHE at Baseline. .
4. Subject has a Grade 2 or Grade 3 HE episode according to the HEGI ([Appendix A](#)) following: a) at least one lactulose treatment with subsequent bowel movement(s) and b) be adequately hydrated (IV fluids at PI discretion).
5. Surrogate decision-maker must be able to read, understand, and provide written informed consent on behalf of the subject on the Institutional Review Board (IRB)/Ethics Committee (EC) approved ICF and provide authorization as appropriate per local privacy regulations.
6. Subject must be able to swallow oral medication (e.g., study drug) without assistance at Baseline.

5.2.1.2 **Exclusion Criteria**

A subject will not be eligible for inclusion in this study if any of the following criteria are met:

Current or Past Medical History

1. Subject has an uncontrolled major psychiatric disorder including major depression or psychoses, as determined by the investigator ([Diagnostic and Statistical Manual of Mental Disorders, 5th., American Psychiatric Association, 2013](#)).

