6.8 Randomization and Blinding

The study drugs will be packaged and labeled identically. In the SSD QD cohorts blinding will be maintained by administering placebo as the second daily dose. Study drug kits will be numbered sequentially and dispensed randomly to the subjects entering the study within each investigational center. Study drug supplies will be distributed to the investigational sites to maintain the randomization ratio within each investigational center.

As a double-blinded study, the investigators, the site staff, the sponsor, and the clinical monitors will not be aware of the treatment assigned to the individual study subjects. Delegated staff members at each investigational center will dispense the study drugs and will collect all used and unused study drug containers as scheduled.

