7.3 Sample Size

Approximately 325 subjects will be randomized in 1:1:1:1:1 ratio to rifaximin SSD tablets [40 mg immediate release (IR)] QD plus lactulose, rifaximin SSD tablets [40 mg immediate release (IR)] BID plus lactulose, rifaximin SSD tablets [80 mg sustained

extended release (SER)] QD plus lactulose, rifaximin SSD tablets [80 mg sustained extended release (SER)] BID plus lactulose and placebo BID plus lactulose.

The sample size estimation is based on cumulative probability distributions of the times from baseline until the first OHE resolution (HEGI score <2) between treatment groups using the log-rank test.

This sample size estimation is based on a previous study with rifaximin ([Sharma 2013](#)). It is assumed that approximately 76% of rifaximin plus lactulose subjects and 51% of placebo plus lactulose subjects will experience OHE resolution over the course of up to 14 days of treatment. With two-sided type I error rate of 0.05, approximately 61 evaluable subjects per treatment group will provide at least 80% power to demonstrate the superiority of rifaximin SSD to placebo using the log-rank test.

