7.5.3 Demographics and Baseline Characteristics

Demographic and baseline characteristics will be summarized descriptively by treatment using the ITT, PP, and safety populations. Demographic characteristics include age, gender, race, ethnicity and weight.

Baseline characteristics include:

- HEGI grade ([Appendix A](#))
- WHC score ([Appendix B](#))
- Serum ammonia levels
- Comprehensive Metabolic/Liver Panel (including ALT, AST, ALP, DBil, TBil, ProTime, INR; total serum protein)
- Hematology: CBC w/Differential
- Alpha fetoprotein (AFP) only in lieu of recent HCC imaging at screening only
- Serum pregnancy test. NOTE: Serum pregnancy tests performed upon hospital admission, prior to study consent, may be used at Screening.
- Urinalysis
- Current Rifaximin use at screening (Yes vs. No)
- Current lactulose use for maintenance of remission at screening (Yes vs. No) and dosage
- Time since first diagnosis of advanced liver disease, defined as first dose date minus date of first diagnosis of advanced liver disease + 1
(randomization date will be used if first dose date is missing)
- Time since first diagnosis of hepatic encephalopathy, defined as first dose date minus date of first diagnosis of hepatic encephalopathy + 1
(randomization date will be used if first dose date is missing)
- Number of HE episodes within the past 6 months
- Factors contributing to HE episodes
- Diabetes at Screening (Yes vs. No)

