7.5.4 Efficacy Endpoint Analyses

Analysis of Primary Efficacy Endpoint

The primary efficacy endpoint is the time to OHE resolution as measured by the HEGI, a modified West Haven Criteria scale. OHE resolution is defined as a HEGI grade of < 2. Resolution of OHE must be confirmed with a repeat evaluation using the HEGI at least 3 and no more than 12 hours after the initial evaluation to demonstrate persistence of resolution. Time to resolution of OHE is defined as the duration between the date/time of first dose of study drug (baseline) and the date/time of first documented resolution of OHE via the HEGI. Subjects who complete the 14 day randomized treatment period without experiencing OHE resolution will be censored at 14 days.

The primary efficacy analysis of time to OHE resolution between each active rifaximin SSD plus lactulose treatment group and the placebo plus lactulose group will be tested using the log-rank test.

Analysis of primary efficacy endpoint will be tested in ITT and PP populations.

Analysis of Secondary Efficacy Endpoints

Analyses of secondary efficacy endpoints will be based on the ITT population.

- Time to OHE resolution defined as a WHC score of 0 or 1
- Time to 1 unit decrease in WHC score during the randomized treatment period.
- Change from Baseline in WHC score at Day 15 or end of blinded treatment period, whichever occurs first.
- Change from Baseline in HEGI score at Day 15 or at end of blinded treatment period, whichever occurs first.
- Time to improvement in HEGI score.
- Length of hospitalization from Baseline to End of Blinded Treatment Phase.

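### The primary log-rank test takes no account of baseline HEGI grade, so it gives up some power and leaves chance grade imbalance uncorrected

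*Combined protocol and SAP*

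**What the plan says.** Section 7.5.4 and the synopsis both state the primary analysis as a pairwise comparison of each active arm with "the placebo plus lactulose group will be tested using the log-rank test". Neither names strata or covariates.

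Entry requires, among other things: "Subject has a Grade 2 or Grade 3 HE episode according to the HEGI" (section 5.2.1.1). Sections 7.5.4 and 8.1.2 define resolution as a HEGI grade below 2.

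On allocation, section 6.8 says: "Study drug supplies will be distributed to the investigational sites to maintain the randomization ratio within each investigational center". Sections 6.7 and 6.8 mention no stratification by grade.

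Section 7.5.3 lists HEGI grade as a baseline characteristic, along with "Current Rifaximin use at screening (Yes vs. No" and others, for descriptive summary by treatment. No stratified test, Cox model, adjusted sensitivity analysis or analysis by grade is planned. The one stratified log-rank result in the document (section 3.3.1) belongs to the earlier study RNLC2131.

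**The concern.** Baseline HEGI grade is the starting value on the outcome scale. To fall below 2, a grade 2 subject has to improve by one grade and a grade 3 subject by two. Grade should therefore predict time to resolution from the definition of the endpoint alone.

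A test that pools the two grades has two weaknesses. It leaves a known source of variation in the comparison, which costs power. It also lets a chance difference in grade mix between arms move the result, with no planned analysis to separate that from a drug effect.

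The second weakness is sharper here because all four comparisons share one placebo arm. An excess of grade 3 subjects on placebo would flatter all four regimens together, and a deficit would count against all four. Keeping the ratio within center does not prevent this: 325 subjects over about 60 sites is 325/60 = 5.4 per site, about one per arm.

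**Working it through.** **Inputs from the documents.** Section 7.3 assumes "approximately 76% of rifaximin plus lactulose subjects and 51% of placebo plus lactulose subjects will experience OHE resolution" by day 14 and states: "With two-sided type I error rate of 0.05, approximately 61 evaluable subjects per treatment group will provide at least 80% power". Section 5.2 gives 65 randomised per arm. Assessments are every 12 hours and censoring is at 14 days.

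**Inputs the documents do not give (assumed).** Share in grade 3: 20%, 35% or 50%. Ratio of the grade 3 to the grade 2 resolution hazard, *h*: 1.0, 0.7, 0.5, 0.35 or 0.25. No loss before day 14.

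**1. The plan's own figure.** Under proportional hazards, HR = ln(1 − 0.76)/ln(1 − 0.51) = 2.00. Expected events with 61 per arm are 61 × (0.76 + 0.51) = 77.5 per comparison. Subjects per arm for 80% power, two-sided 0.05:

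- Schoenfeld: 66 events, 66/1.27 = 52 per arm
- Freedman: 71 events, 71/1.27 = 56 per arm
- Two proportions: 58 per arm, or 65 with continuity correction

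None of these gives exactly 61, but power at 61 per arm is 86.3% (Schoenfeld), 83.5% (Freedman) or 82.6% (two proportions). The claim of at least 80% is met by the unstratified test.

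**2. Chance imbalance in grade.** With 40% in grade 3, the SD of the difference in share between two arms of 65 is √(2 × 0.4 × 0.6/65) = 8.6 points. The probability of a gap of 10 points or more is 2 × [1 − Φ(10/8.6)] = 24%, or about 12% in each direction. For shares of 20% to 50% the two-sided probability is 15% to 25% per comparison.

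**3. Power with and without stratification.** With a share *q* in grade 3, each arm's cumulative hazard *H* was solved from (1 − q)(1 − e^(−H)) + q(1 − e^(−hH)) = 0.51 or 0.76. The plan's marginal rates therefore hold in every scenario. Simulation used 61 per arm, a 28-point 12-hour grid and 4,000 runs per scenario. The Monte Carlo standard error is about √(0.87 × 0.13/4000) = 0.5 points. Entries are power, unstratified → stratified:

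| *h* | 20% grade 3 | 35% grade 3 | 50% grade 3 |
|---|---|---|---|
| 1.0 | 86.4 → 85.7 | 86.0 → 85.6 | 86.4 → 85.4 |
| 0.7 | 86.5 → 87.1 | 86.3 → 86.7 | 85.4 → 86.3 |
| 0.5 | 86.6 → 88.2 | 86.2 → 88.6 | 86.5 → 89.2 |
| 0.35 | 85.5 → 89.6 | 86.6 → 91.8 | 87.9 → 93.7 |
| 0.25 | 87.0 → 91.7 | 88.6 → 96.1 | 88.8 → 97.5 |

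Simulated type I error was 4.2% to 5.5% across both tests.

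**4. Power when the imbalance goes against the drug.** These are the runs in which the active arm had at least 10 points more grade 3 subjects than placebo (6% to 12% of runs, so the standard error here is 2 to 3 points):

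| *h* | Unstratified | Stratified |
|---|---|---|
| 0.7 | 79-83% | 84-89% |
| 0.5 | 75-79% | 89-90% |
| 0.35 | 65-73% | 89-93% |

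**5. In terms of sample size.** At 65 per arm with 30-50% in grade 3, power goes from 88-89% to 91% at *h* = 0.5 and from 90% to 94-96% at *h* = 0.33. The squared ratio of mean Z statistics, stratified over unstratified, gives the equivalent gain in patients: 7-9% and 18-27%. At *h* = 0.7 the power gain is under 1 point.

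**The case against.** The best reply is that nothing here is broken. The unstratified test controls type I error, exceeds its stated power, and addresses the hypothesis in section 7.2, which concerns the pooled time distributions. Chance imbalance is random error that the test already allows for. This is a Phase 2 dose-ranging trial. Section 7.5.3 will show grade by arm, and two secondary endpoints (time to improvement in HEGI score, time to a 1-unit decrease in WHC score) measure change from the starting grade.

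The gain also depends wholly on two unstated inputs. Subjects must be able to swallow tablets unaided, and grade is taken after lactulose and hydration, so grade 3 may be uncommon. At 65 per arm with 20% in grade 3, the sample-size gain is 0%, 4% and 14% at *h* = 0.7, 0.5 and 0.33. With 10% in grade 3 it is 0%, 2% and 6%.

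Most of this stands. The loss is one of efficiency. Any distortion is conditional on the imbalance that occurs, and is not bias averaged over randomisations. The stratified hazard ratio is a within-grade quantity (2.05 to 2.09 at *h* = 0.5, against 2.00 pooled) and should be labelled as such.

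The mitigations do not answer the point, however. A baseline table can reveal an imbalance but cannot correct the primary result, and the secondary endpoints do not adjust the primary one. An adjustment chosen after seeing an imbalance would carry little weight.

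**Conclusion.** The concern holds. Baseline HEGI grade enters neither the randomisation nor the primary test, although it fixes how far each subject starts from the event.

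The average cost ranges from nothing, if grade is weakly prognostic or grade 3 is rare, through 2-3 points of power at *h* = 0.5, to about 9 points at *h* = 0.25 with half the subjects in grade 3. The stronger reason to act is the unlucky allocation: with a gap of 10 points or more against the drug, unstratified power at *h* = 0.5 drops below the planned 80% while stratified power stays near 90%. If grade had no prognostic value at all, stratifying would cost up to 1 point in these simulations.

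All of these sizes rest on the assumed grade 3 share and hazard ratio, proportional hazards within grade, and no loss before day 14. The trial is not invalid without the change; it is a low-cost improvement that should be made.

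**What to change.** In section 7.5.4 and the synopsis, make the primary test of each active arm against placebo a log-rank test stratified by baseline HEGI grade (2 vs 3). Report with it a Cox hazard ratio and 95% CI using the same stratum, described as a within-grade effect. Keep the unstratified log-rank test as a sensitivity analysis. Align section 7.2 by stating the null hypothesis as equal time distributions within each grade. The sample size in section 7.3 can stay, since it meets its target without stratification.

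Current rifaximin use at screening could be a covariate in a supportive Cox model if the cells are not sparse. Its benefit has not been quantified and the main change does not need it.

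Make the change before the interim analysis in section 7.6, because designated sponsor staff are unblinded there once at least 10 subjects per group have completed blinded treatment. The cost is a few sentences, with no new data, subjects or visits. If enrolment has not begun, stratifying the randomisation by grade would limit the imbalance itself, at the price of a change to the randomisation system.

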7.5.5 Safety Endpoints Analyses

All safety analyses will be performed for the Safety Population. Each analysis will consist of a summary of data within each treatment group.

Adverse Events:

Adverse events will be coded using the Medical Dictionary for Regulatory Affairs (MedDRA) coding dictionary. Treatment-emergent AEs will be defined as any event with a start date occurring on or after initial treatment (baseline visit) or, if pre-existing, worsening after initial treatment (baseline).

The incidence of treatment-emergent AEs will be summarized for each treatment group by body system and MedDRA preferred term. If a subject reports the same AE more than once, then that subject will only be counted once for the summary of that AE, using the most severe intensity.

Treatment-emergent AEs will be summarized as follows:

- Number and percentage of subjects experiencing TEAEs;
- Number and percentage of TEAEs by relationship to study treatment (i.e. related or unrelated);
- Number and percentage of TEAEs by severity (i.e., mild, moderate or severe);
- Number and percentage of subjects experiencing serious AEs (SAEs);
- Number and percentage of subjects experiencing study drug-related SAEs;
- TEAE leading to permanent treatment discontinuation;
- TEAEs with an outcome of death.

The incidence of treatment-emergent AEs of infections, such as SBP, UTI, pneumonia, bacteremia and cellulitis will be summarized by each treatment group.

If a subject reports the same AE more than once, then that subject will only be counted once for the summary of that AE, using the most severe intensity. Severity and AE leading to early termination will also be presented for these infection AEs.

All SAEs and AEs leading to premature withdrawal from the study, and all deaths, will be listed.

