- **Cohort 4 (Treatment D)** will enroll 65 subjects with OHE to be administered 80 mg sustained extended release (SER) rifaximin SSD twice daily (BID) and lactulose**.
- **Cohort 5 (Treatment E)** will enroll 65 subjects with OHE, to be administered SSD placebo twice daily (BID) and lactulose**.

All subjects who complete the blinded randomized treatment phase (defined as confirmed resolution of OHE), will continue on to the safety follow-up period receive 30 days of open-label treatment with Xifaxan® 550 mg upon hospital discharge, regardless of the treatment arm to which they were previously randomized.

An interim analysis will be conducted when at least 10 subjects per treatment group have completed participation in the blinded treatment period of the study. The unblinded interim results will be reviewed by a few designated members of the Sponsor's team who do not have direct involvement with the ongoing study. The interim results will not be shared outside of the small designated team, and no changes will be made to the ongoing study based on the interim study results.

*Blinding will be maintained in the QD SSD cohorts by administering placebo as the second daily dose. All subjects will receive two tablets per day at 12 hour (± 2 hour) intervals.

** The adult, oral dosage is 2 to 3 tablespoons (30 to 45 mL, containing 20 to 30 g of lactulose) three times daily. The dosage should be adjusted to produce 2 to 3 soft stools daily or per PI discretion. Rectal lactulose may be administered in lieu of oral lactulose. Bristol stool type will still be assessed as required by the protocol for subjects dosed with rectal lactulose. Dose amount and frequency for rectal lactulose should be administered according to product label or per PI discretion.

Diagnosis and Main Criteria for Inclusion:

1. Male or female at least age 18 or older at the time of consent.
2. Females of childbearing potential, defined as a female who is fertile following menarche, must have a negative serum pregnancy test at screening and agree to use an acceptable method of contraception throughout their participation in the study. NOTE: Serum pregnancy tests performed upon hospital admission, prior to study consent, may be used at Screening.

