The primary endpoint in this study is time to resolution of OHE per the HE Grading Instrument (HEGI). OHE status will be evaluated every 12 hours (+/- 2 hours) after randomization. Resolution is defined as a HEGI score < 2.

Statistical Methods:

The primary efficacy endpoint is time to OHE resolution. OHE resolution is defined as a HEGI score < 2. Time to resolution of OHE is defined as the duration between the date/time of first dose of study drug and the date/time of first resolution of OHE. Subjects who complete the blinded randomized treatment period without experiencing OHE resolution will be censored at 14 days post first dose.

The primary efficacy analysis of time to OHE resolution between each active rifaximin SSD plus lactulose treatment group and the placebo plus lactulose group will be tested using the log-rank test.

Analysis of primary efficacy endpoint will be tested in intent-to-treat (ITT) and per protocol (PP) populations.

- The ITT population will include all randomized subjects who received at least one dose of blinded treatment drug.
- The PP population will include all ITT subjects who remain in study through the end of the blinded randomized treatment period and who have not deviated from the protocol in any way likely to seriously affect the primary outcome of the study. Important protocol deviations will be identified prior to locking the study database.

The incidence of treatment-emergent AEs will be summarized for each treatment group by body system and MedDRA preferred term. If a subject reports the same AE more than once, then that subject will only be counted once for the summary of that AE, using the most severe intensity.

The incidence of treatment-emergent AEs of infections, such as spontaneous bacterial peritonitis (SBP), urinary tract infection (UTI), pneumonia, bacteremia and cellulitis, will be summarized by each treatment group. If a subject reports the same AE more than once, then that subject will only be counted once for the summary of that AE, using the most severe intensity. Severity and AE leading to early termination will also be presented for these infection AEs.

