5.0 STUDY DESIGN

5.1 Description of Study Design

Study RNHE2041 is a Phase 2, randomized, double-blind, placebo controlled, multicenter study evaluating the efficacy and safety of rifaximin SSD tablets (40 mg IR and 80 mg SER) plus lactulose in subjects hospitalized with OHE. Subjects who have liver cirrhosis and OHE, defined as a score of 2 or 3 on the Hepatic Encephalopathy Grading Instrument [[\(HEGI\); Appendix A](#)], are eligible for enrollment. Subjects who successfully meet the inclusion/exclusion criteria will enter the treatment period and will be randomized in a 1:1:1:1:1 ratio into 1 of 5 treatment groups as noted below. The blinded treatment period starts upon randomization following hospital admission.

Subjects will be on blinded treatment for up to 14 days. All subjects who complete the blinded randomized treatment phase (defined as confirmed resolution of OHE), will continue on to the safety follow-up period and receive 30 days of open-label treatment with Xifaxan® 550 mg upon hospital discharge, regardless of the treatment arm to which they were previously randomized. If subjects remain hospitalized following OHE resolution, standard of care treatment (which may include Xifaxan® 550 mg) should be given until hospital discharge. Open-label drug should only be dispensed to subjects upon hospital discharge. Please note this may be on a different day than OHE resolution.

- Treatment A: 40 mg immediate release (IR) rifaximin SSD tablet once daily (QD) and lactulose*.
- Treatment B: 40 mg immediate release (IR) rifaximin SSD tablet twice daily (BID) and lactulose*.

- Treatment C: 80 mg sustained extended release (SER) rifaximin SSD tablet once daily (QD) and lactulose*.
- Treatment D: 80 mg sustained extended release (SER) rifaximin SSD tablet twice daily (BID) and lactulose*.
- Treatment E: SSD placebo tablet twice daily (BID) and lactulose*.

*Oral Lactulose will be administered according to the product label, with dosage adjusted to produce 2 to 3 soft stools daily or per PI discretion. Rectal lactulose may be administered in lieu of oral lactulose. Bristol stool type will still be assessed as required by the protocol for subjects dosed with rectal lactulose. Dose amount and frequency for oral and rectal lactulose should be administered according to the product label or per PI discretion.

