8.0 STUDY METHODS

8.1 Study Visits

Following identification of a potential subject, the Investigator (or designee) will explain the purpose of the study, procedures, risks/benefits, and subject responsibilities to the potential subject's caregiver. The subject's ability to meet the requirements of the study will be determined in discussions with the caregiver. If the caregiver consents on behalf

Clinical Study Protocol, Amendment 3, dated 08 January 2020

CONFIDENTIAL

Page 38

of the subject the person obtaining written consent will sign and date the IRB/EC-approved ICF, at which point the subject is considered part of the study population. The original signed document will be retained in the subject records, and a copy will be provided to the subject/caregiver. In addition, the applicable privacy regulation requirements must be met.

Study Visit procedures are outlined in [Table 1](#).

Table 1: Study Design and Schedule of Assessments

	Blinded Randomized Treatment Period		Hospital Discharge	Open-label Safety Follow-up Period		
	Screening & Baseline	Treatment Period		Follow-up ⁴ Visit 1	Follow-up ⁴ Visit 2	Follow-up ⁴ Visit 3/ EOS ⁸
Study Day	Study Day 1	Study Day 2 Up to Study Day 15		Day 7 Post Resolution (±2)	Day 14 Post Resolution (±2)	Day 30 Post Resolution (±2)
Informed Consent	X					
Review inclusion / exclusion criteria	X					
Medical History and Demographics	X					
Record Concomitant Medications	X	X	X	X	X	X
Discontinue use of prohibited medications	X					
Vital Signs and Weight (kg)	X	X		X	X	X
Height (cm)	X					
Physical Examination	X	X ²		X	X	X
Clinical Laboratory Tests/ Urinalysis	X ⁵	X		X	X	X
Serum/Urine Pregnancy Test	X ⁶					X ⁶
HEGI ¹	X	X ²		X	X	X
WHC ¹	X	X ²		X	X	X
CBI ¹	X			X	X	X
Randomize Subject in EDC	X					
Dispense/Administer 1 st Dose of Blinded Study Drug		X ²				
Record dates/times of study drug dosing		X				
Record Bristol Stool Appearance		X				
Record lactulose use (dosing time and amount) dates/times of lactulose use	X	X		X ³	X ³	X ³
Assess Open-Label Dosing Compliance				X ³	X ³	X ³
Record Adverse Events	X	X	X	X	X	X
Dispense Open Label Xifaxan® 550mg and Review Dosing Instructions			X ⁷			
CLDQ ¹				X	X	X

Abbreviations: EOS = end of study

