9.3.1 Time Period for Detecting and Reporting of AEs and SAEs

From the time of informed consent through study completion/early termination, including the 30-day open-label safety follow-up period.

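### Section 7.5.5 gives treatment-emergent AEs a start but no end, so the by-arm AE and infection tables, read literally, mix blinded time with open-label Xifaxan time whose length depends on resolution

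*Combined protocol and SAP*

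**What the plan says.** Section 7.5.5 defines the window by its start only: "Treatment-emergent AEs will be defined as any event with a start date occurring on or after initial treatment (baseline visit", or by later worsening of a pre-existing event. The output is descriptive: "Each analysis will consist of a summary of data within each treatment group". The synopsis says of infections that "pneumonia, bacteremia and cellulitis, will be summarized by each treatment group", and Section 7.5.5 repeats this. Neither place splits by phase, uses time at risk, or describes a separate open-label AE table.

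Collection is longer than the blinded phase. Section 9.3.1 sets it as "From the time of informed consent through study completion/early termination, including the 30-day open-label safety follow-up period", and the row "Record Adverse Events" in Table 1 (Section 8.1) is marked in every column, including discharge and all three follow-up visits.

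Entry to the open-label phase depends on outcome: "All subjects who complete the blinded randomized treatment phase (defined as confirmed resolution of OHE), will continue on to the safety follow-up period" (synopsis; Section 5.1 has the same condition). All of them receive Xifaxan whatever their randomized arm, and Section 5.1 allows it as standard of care between resolution and discharge. Follow-up visits are timed from resolution, the first at "Day 7 Post Resolution".

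The endpoint lists point the other way. The synopsis places TEAEs and infections under its Efficacy Phase heading, apart from the open-label endpoints, and describes the blinded phase as covering both safety and efficacy. In Section 7.1 the laboratory and vital-sign endpoint stops at OHE resolution.

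**The concern.** Safety of rifaximin SSD is a secondary objective, and these tables are its main by-arm output. If 7.5.5 is programmed as written, an infection late in open-label Xifaxan counts in the placebo column when the subject was randomized to placebo.

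Two things then go wrong. First, a period in which all arms share the same drug dilutes any real SSD-versus-placebo difference. Second, the length of observation depends on resolution, the outcome that SSD is meant to change. An arm that resolves more subjects has less blinded time and more later time, so a crude proportion can differ between arms with no drug effect on AEs.

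The window is also unsettled for subjects who stop during blinded treatment. The withdrawal criteria in Section 5.2.1.2 ask them back for a visit 30 days after stopping, Section 8.1.3 exits them from the study, and Section 9.4 requires SAEs within 30 days of stopping drug to be reported whether or not they resolved.

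**Working it through.** **The plan's own figures.** The documents state no safety figure. The only one sharing these inputs is the sample size in Section 7.3: 61 evaluable per group for at least 80% power at 76% versus 51%. With exponential times to resolution, simulated log-rank power at 61 per group is about 86%, consistent with that statement.

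**Inputs.** From the documents: resolution by 14 days of 76% (SSD) and 51% (placebo), and 30 days of follow-up after resolution. Assumed: exponential time to resolution, constant daily AE rates *rb* (blinded) and *ro* (later), no deaths or dropout. Because the follow-up rules conflict, later follow-up is taken either for resolvers only or for everyone.

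**Resolution rate.** λ = −ln(1 − p)/14. SSD: −ln(0.24)/14 = 0.1019 per day. Placebo: −ln(0.49)/14 = 0.0510. The ratio is 2.0.

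**Observed time.** Mean blinded days = p/λ: 7.5 (SSD) and 10.0 (placebo).
- Resolvers only: later days are 30 × 0.76 = 22.8 and 30 × 0.51 = 15.3. The later share is 22.8/30.3 = 75% and 15.3/25.3 = 60%.
- Everyone followed: 30/37.5 = 80% and 30/40.0 = 75%.

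**Incidence of at least one event.** Let a = λ + rb, A = (λ/a)(1 − e^(−14a)) and B = e^(−14a).
- Pooled, resolvers only: 1 − (A·e^(−30ro) + B)
- Pooled, everyone: 1 − (A + B)·e^(−30ro)
- Blinded only: 1 − (A + B)

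Example, 1% per day throughout, no drug effect, resolvers only:
- SSD: A = 0.7207, B = 0.2086, incidence 1 − (0.7207 × 0.7408 + 0.2086) = 0.2575.
- Placebo: A = 0.4798, B = 0.4260, incidence 0.2185.
- Ratio 1.18.

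**SSD/placebo ratios.** In the halved columns only the SSD blinded rate is halved.

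| Daily rate, blinded / later | No effect, pooled, resolvers only | No effect, pooled, everyone | Halved, pooled, resolvers only | Halved, pooled, everyone | No effect, blinded-only count |
|---|---|---|---|---|---|
| 0.5% / 0.5% | 1.19 | 0.94 | 1.05 | 0.86 | 0.75 |
| 1% / 1% | 1.18 | 0.95 | 1.04 | 0.87 | 0.75 |
| 2% / 2% | 1.16 | 0.96 | 1.04 | 0.89 | 0.76 |
| 5% / 5% | 1.12 | 0.98 | 1.02 | 0.95 | 0.77 |
| 2% / 1% | 1.06 | 0.92 | 0.87 | 0.80 | 0.76 |
| 3% / 1% | 0.995 | 0.90 | 0.79 | 0.75 | 0.76 |
| 5% / 1% | 0.94 | 0.88 | 0.71 | 0.71 | 0.77 |

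If the SSD blinded rate is doubled at equal rates, the pooled ratio is 1.24 to 1.46 (resolvers only) or 1.02 to 1.11 (everyone).

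**Is a cut at the end of blinded treatment enough?** No. The last column shows 0.75 to 0.77 with no effect, because placebo subjects stay blinded longer. Events per patient-day within the blinded window recover 0.5, 1.0 and 2.0 exactly when risk is constant. If risk is multiplied by d each day, the no-effect rate ratio is [∫dᵗS(t)dt / ∫S(t)dt] for SSD over placebo on 0 to 14 days, with S(t) = e^(−λt). It is 1.04 at d = 0.95 and 1.20 at d = 0.70.

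**The case against.** The strongest reply is that blinded scope is already intended: the synopsis lists TEAEs and infections under the blinded phase, with open-label endpoints listed separately. That is good evidence of intent, and a reader should not infer that the sponsor plans to pool. But Sections 7.1 and 7.5.5 do not carry the heading into a cut-off, and Sections 7.5.6 and 7.5.7 summarize laboratory values and vital signs at each visit. The analysis text therefore does not apply the lists' scope even there.

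A reader might also infer that pooling would turn a real infection benefit into an apparent excess. The documents do not support that as a general statement. It needs resolvers-only follow-up and a later AE rate equal to the placebo blinded rate. If risk is higher during the acute admission than afterwards, which is at least as plausible, the halved case reads 0.87 to 0.71: diluted but visible. For SAEs, the reporting rule in Section 9.4 makes the everyone-followed model the closer one.

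Three further points stand. The model ignores deaths and dropout, although the introduction cites about 18% mortality in HE admissions. Sampling error is larger than the bias: with 65 per arm and incidences of 0.2575 and 0.2185, the 95% interval for the ratio extends by a factor of about 1.86 either way. And all SAEs, deaths and AE withdrawals are listed individually, so nothing is lost irrecoverably.

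**Conclusion.** The point holds as a gap and an inconsistency in the specification of the main safety tables. Taken literally, Section 7.5.5 pools blinded time with a longer period largely on a drug common to all arms, and the length of that period depends on resolution. Under the plan's resolution rates the distortion with no drug effect is modest and of either sign: 1.12 to 1.19, 0.94 to 0.98, or 1.06 to 0.94, depending on who is followed and how risk changes after the blinded phase. A true halving is attenuated in every case examined. Direction and size rest on AE rates that the documents do not give, on exponential resolution, and on no deaths or dropout. Safety is summarized descriptively, so no test and no primary conclusion changes. What is affected is how the by-arm safety tables can be read.

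**What to change.** In Section 7.5.5:

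- Make the main by-arm SSD-versus-placebo summary of TEAEs, infections and SAEs count events with onset from first to last blinded dose, with rates per patient-day beside counts and percentages.
- If a lag after the last blinded dose is wanted, use the same fixed lag for every subject and include it in the denominator. A lag cut at the first Xifaxan dose would again make the window depend on resolution.
- Tabulate events after blinded treatment separately, by prior arm.
- Keep a whole-study table as supportive, so that late effects of blinded drug remain visible.
- Reconcile Sections 5.2.1.2, 8.1.3 and 9.4 on follow-up of subjects who stop during blinded treatment, and state the resulting AE window.

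The cost is some wording and one more set of tables; the dates needed are already recorded. Patient-day rates assume roughly constant risk within the window. If risk falls over time, the no-effect ratio is 1.04 to 1.20, and the table should carry that caution. The change should be made before unblinding.
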